12.3 Retention of Records and Documentation

The clinical investigator will be required under FDA Regulation 21 CFR §812.140(d) to retain all copies of the records for a period of 2 years after the latter of two dates: (1) the date on which the investigation is terminated or completed, or (2) the date that records are no longer required for purposes of supporting a premarket application. In all cases, the investigator must contact the sponsor prior to disposing of any records related to the clinical investigation. Included in the records to be maintained are signed Clinical Protocols, source records for any data, copies of any paper Case Report Forms, signed consent forms, ethics committee approval letters, product use records, and any correspondence concerning the clinical trial.

12.4 Data Management

The processing of all data on the Case Report Forms will be the responsibility of the sponsor. All data recorded from the Case Report Forms to data analysis software will be subject to independent verification for accuracy. Comparison of the data entries will then be performed and any resulting discrepancies adjudicated by an independent third person with reference to the Case Report Form. All data queries will be resolved with the assistance of monitoring staff and documented in writing as described above.

The Monitor will use controlled Standard Operating Procedures in all aspects of data management, data verification, archiving and retention.

12.5 Collection of Medical History Data for Patient

The following medical history data will be collected from each subject:

- Normal or abnormal eyes, ears, nose, throat
- Normal or abnormal neurological
 - CVA (cerebrovascular accident)
 - TIA (transient ischemic attack)
 - Shunt for hydrocephalus
 - CEA (carotid endarterectomy)
 - Myasthenia gravis
 - Seizures
 - Multiple sclerosis
 - Encephalitis

- Meningitis
- Subdural hematoma
- Epidural hematoma
- Normal or abnormal gastrointestinal
- Normal or abnormal respiratory
 - Current/past tobacco use
- Normal or abnormal cardiovascular
- Normal or abnormal genitor-urinary
- Normal or abnormal musculoskeletal
- Normal or abnormal dermatological
- Normal or abnormal endocrine
 - Diabetes
 - Hypothyroidism
 - Hyperthyroidism
- Drug/alcohol use
- Normal or abnormal hematological
- Normal or abnormal hepatic
- Allergies and drug intolerance

12.6 Collection of Data by Device

Each second, the COOLSTAT device will be automatically collecting air flow rate, air temperature supplied to subject, air humidity supplied to subject, air pressure, and the subject's core temperature data. This data is automatically stored to a micro SD card, with a new file started with each device power-on. The SD card is embedded in the device and is not accessible unless the device external housing is removed, which would require the use of tools. A serial data logger will be used to transfer device data from the CoolStat to a secure data storage cloud. This will allow the study Sponsor and monitor to review and verify the source data in a timely manner, without requiring the retrieval of devices. The data collected by the COOLSTAT has a time and date stamp, but no other subject identifying information. Therefore, in order to tie the data to a specific subject, the time and date stamp will be matched to the time that was manually recorded when the subject began COOLSTAT therapy. All data collected by the COOLSTAT will be subject to audit by the study monitor and may not be used in analysis of the effectiveness of cooling if not verifiable.

To validate the data saved by the COOLSTAT, testing will be performed on each COOLSTAT unit to ensure the expected outputs result from a range of inputs. The data for each sensor (flow rate, air temperature, humidity, and pressure, and subject's core temperature) is compared with readings from an external calibrated sensor. Multiple

conditions will be tested for each sensor to ensure the saved data are accurate over expected operating ranges.

The COOLSTAT's screen displays the subject's current temperature measurement for reference during the trial (this data is automatically collected by the COOLSTAT) – this measurement is the same as the core temperature displayed on the hospital monitor.

12.7 Collection of Manual Data

Subject core and tympanic temperatures, blood pressure, intracranial pressure (when available), suctioned water volume, and level of shivering will be monitored and recorded in the Therapy and Observation Record throughout the therapy period. Data to be collected during the course of the study is detailed in Section 9.0.

Data collection will occur at a minimum 5 minute intervals for the first 30 minutes of cooling, 30 minute intervals during the first 8 hours, and then every 2 hours for the remaining 16 hours (if applicable). During Phase 2, data collection will occur at a minimum of 15 minute intervals. After Phase 2, manual data will continue to be collected at a minimum of every 4 hours for the next 22 hours.

13.0 Statistical Analysis Plan

The primary efficacy analysis for cooling performance will be based on the evaluable populations of subjects who undergo cooling treatment with the COOLSTAT System. Analysis will be performed on treatment initiated and treatment completed populations. Subjects who achieve normothermia (core temperature $\leq 37.5^{\circ}\text{C}$) within 4 hours of starting COOLSTAT treatment and maintain normothermia for the duration of the treatment will be determined to have been treated successfully.

The primary efficacy analysis for temperature maintenance will be based on the evaluable population of subjects who maintain normothermia (core temperature between 36°C and 37.5°C) for at least 80% of the time following the initial achievement of 37°C will be determined to have been treated successfully.

The proportion of subjects fulfilling success criteria and 90% confidence intervals will be reported and compared to the a priori minimum acceptable criteria:

- at least 75% of the subjects will reach normothermia (core temperature $\leq 37.5^{\circ}\text{C}$) within 4 hours of starting COOLSTAT cooling, and
- at least 75% of the subjects' core temperatures remain between 36°C and 37.5°C for 80% of the steady state time following the initial achievement of 37.5°C .

Continuous measurements will be summarized using the mean and standard deviation. Categorical variables will be reported using percentages and confidence intervals. Data collected will be plotted to demonstrate the change in core temperature from baseline.

An exploratory analysis of participant subgroups will be performed, stratified by stroke presentation (ischemic versus hemorrhagic). Cooling performance and AEs will be evaluated by subgroup.

Double nostril air flow and single nostril air flow subjects will not be merged or directly compared. The results from subjects treated with single nostril flow will be analyzed separately from subjects treated with double nostril air flow.

Subjects 1 through 20 will be assigned to the double nostril air flow treatment group:

- Subjects 1 through 10 will be treated for 8 hours (N=10)
- Subjects 11 through 20 will be treated for 24 hours (N=10)

Subjects 21 through 30 will be assigned to the single nostril air flow treatment group

- Subjects 21 through 30 will be treated for 24 hours (N=10).
- Subjects 21 through 30 will be treated using a dose escalation model:
 - Dosing for this cohort (flow rate) will begin at 30 LPM.
 - The dose will be increased by 10 LPM if 3 consecutive subjects complete the study protocol with no serious adverse events (as listed in section 10.5) or unanticipated adverse device events.
 - Up to three doses will be evaluated in this cohort (30 LPM, 40 LPM, 50 LPM).
- The purpose of this cohort is to assess the safety of and optimal dose for the single nostril air flow configuration of the CoolStat.
- Each subject will be examined for adverse events, serious adverse events, and unanticipated adverse device events by an intensivist or otolaryngologist within 24 hours of completing CoolStat therapy.
- Each flow rate cohort must be evaluated by an intensivist or otolaryngologist prior to advancing the protocol to the next increased flow rate cohort.

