Statistical Methodology	
The primary efficacy analysis for temperature maintenance will be based on the evaluable population of subjects who achieve normothermia by 4 hours and continue cooling treatment with the COOLSTAT System.
 
The proportion of subjects fulfilling success criteria and 90% confidence intervals will be reported and compared to the a priori minimum acceptable criteria:
 
 • at least 75% of the subjects will reach normothermia (core temperature $\leq 37.5^{\circ}\text{C}$) within 4 hours of starting COOLSTAT cooling, and • at least 75% of the subjects' core temperatures remain between 36°C and 37.5°C for 80% of the steady state time following the initial achievement of 37.5°C. 
All adverse events (AEs) reported during the study will be presented in tabular format to include: time of onset, whether or not the patient continued in the study, the nature of intervention and resolution. The potential contribution to the AE by the device will be assessed by the attending physician who reports the AE and the investigator.

Data Safety Monitoring Board	
A DSMB will be formed to monitor this study. The DSMB will meet: 1) before any subjects are enrolled (to review the study), 2) after the first 5 subjects (all with ICP monitoring), 3) after the first 10 subjects (before proceeding to 24-hour

upon being reconnected to the CoolStat is $\leq 37.5^{\circ}\text{C}$. If the subject's temperature is $> 37.5^{\circ}\text{C}$ upon being reconnected to the device, the device will be given up to an additional 4 hour-period to bring the patient to normothermia ($\leq 37.5^{\circ}\text{C}$). Once the subject's core temperature is $\leq 37.5^{\circ}\text{C}$, the device will be considered in steady state.

cooling treatment), 4) after each 6-month period of study, 5) at the end of the study, and 6) after any serious adverse event.

A clinical monitor will also be used to periodically visit the study sites and monitor the activities of the study to ensure that the study protocol, consent activities and data collection are being completed in accordance with specified procedures.

The Clinical Monitor and DSMB will be comprised of:

- [name] - Clinical Monitor
- [name] (Johns Hopkins) - Chair of DSMB - Voting Member
- [name] (Johns Hopkins) - DSMB Voting Member
- [name] (UMMC) - DSMB Voting Member
- [name] (UMMC) - DSMB Voting Member
- [name] (UMMC) - PI (Non-Voting Member)

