6.3 Primary Efficacy Endpoint and Success Criteria

This feasibility study should confirm that the COOLSTAT system has the ability to safely and adequately achieve and maintain normothermic cooling therapy with its control system over a specified period for subjects who were enrolled in the study.

This cooling aspect of the trial will be considered a success if at least 75% of the subjects achieve the following criteria:

- Cooling Performance: The subjects reach normothermia (core temperature $\leq 37.5^{\circ}\text{C}$) within 4 hours of starting COOLSTAT cooling.
- Temperature Maintenance: The subjects are held within a 1.5°C temperature band, between $36^{\circ}\text{C} - 37.5^{\circ}\text{C}$, for 80% of the steady state time following the initial achievement of 37.5°C .³

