6.6 Sample size calculations

The sample size was determined from the calculation below, using the following assumptions:

$$n = \left[\frac{z_{\alpha} \sqrt{p_0(1-p_0)} + z_{\beta} \sqrt{p_1(1-p_1)}}{p_1 - p_0} \right]^2$$

n: minimum sample size

$p_0 = 0.9$ Assumed proportion of subjects successfully cooled

$p_1 = 0.75$ Lowest acceptable proportion of subjects successfully cooled

$\delta = |p_1 - p_0| = 0.15$ Difference between ideal and minimum acceptable

Confidence (α): 90%

$$z_{95} = 1.28$$

Statistical Power (β): 80%

$$z_{80} = 0.84$$

n = 25 subjects completing treatment, therefore a sample size of 30 subjects was selected to allow for dropouts. The study will enroll up to 70 subjects, accounting for a 55% expected post-consent screen failure rate. Enrollment will stop once the 30th subject receives COOLSTAT therapy.

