6.10 Transition from 8-hour Cooling to 24-hour Cooling

The first 10 subjects will only be cooled for an 8-hour period, the results of which will be reviewed by the DSMB. For these first 10 subjects, if the subject still requires cooling at the end of 8 hours, the clinical site normothermia standard of care protocol will be used. If approved by the DSMB, the remaining subjects will transition to 24-hour cooling only upon satisfying all of the following criteria:

- No significant adverse events (SAEs) attributed to CoolStat
- CoolStat satisfied primary efficacy endpoint and success criteria on first 10 subjects (as specified herein):
 - 8 out of 10 subjects were cooled to $\leq 37.5^{\circ}\text{C}$ within 4 hours (based on final study endpoint of 75% subject achievement of this criteria)
 - 8 out of 10 subjects had core temp maintained between 37.5°C and 36°C for 80% of the steady state time following the initial achievement of 37.5°C .
- No findings of concern from ENT visual exam of upper airway post cooling
- Tympanic $> 34^{\circ}\text{C}$ and $< 39^{\circ}\text{C}$ during 8 hours of cooling, with no sustained period of more than 5 minutes $< 34^{\circ}\text{C}$ or more than 4 hours $> 39^{\circ}\text{C}$.
- No sustained increase of systolic blood pressure for > 5 minutes despite standard of care interventions that were above UMMC standard limits (specific to the indication being treated).
- DSMB reviews CRFs and agrees to increasing test period to 24 hours

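### Section 13.0 misstates the primary success rules: its maintenance population is, as worded, the outcome itself, and the documents do not settle which denominator is compared with 75%

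*Combined protocol and SAP*

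**What the plan says.** **Maintenance, Section 13.0.** "The primary efficacy analysis for temperature maintenance will be based on the evaluable population of subjects who maintain normothermia" in the 36–37.5°C band "for at least 80% of the time following the initial achievement of 37°C will be determined to have been treated successfully". The bulleted criterion a few lines later in the same section starts at 37.5°C and counts steady state time only.

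**Maintenance, elsewhere.**
- Synopsis (Section 1.0, Statistical Methodology): the "evaluable population of subjects who achieve normothermia by 4 hours and continue cooling treatment with the COOLSTAT System".
- Section 6.3: "This cooling aspect of the trial will be considered a success if at least 75% of the subjects achieve the following criteria". Section 13.1 likewise refers only to the subjects, and neither section defines an analysis set.
- Section 6.10, on moving to 24-hour cooling, requires that "CoolStat satisfied primary efficacy endpoint and success criteria on first 10 subjects (as specified herein" and spells this out as 8 of 10 subjects for cooling and 8 of 10 for maintenance.
- The hypothesis and methodology rows of the synopsis, and Sections 6.3, 6.10 and 13.1, all use 37.5°C and steady state time. Section 9.3 limits the analysis to steady state time.

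**Cooling, Section 13.0.** "Analysis will be performed on treatment initiated and treatment completed populations". Success is reaching 37.5°C or below within 4 hours, but the sentence goes on to require that subjects "maintain normothermia for the duration of the treatment will be determined to have been treated successfully". The bulleted cooling criterion, 6.3 and 13.1 have no such condition.

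**Related text.** Section 9.3 takes subjects who are not normothermic at 4 hours off the device as treatment failures, but lets the investigator continue cooling if the subject is approaching target. Section 6.6 arrives at 25 "subjects completing treatment, therefore a sample size of 30 subjects was selected to allow for dropouts".

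**The concern.** Both 75% criteria are proportions, so each needs a fixed numerator rule and a fixed denominator. Section 13.0 is where an analyst would look for them, and it gives neither cleanly.

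For maintenance, its only population statement is the success definition. Turning to the synopsis gives 4-hour responders still on the device, so a subject who never reached normothermia cannot count against maintenance. Under the 6.10 count that subject does count against it. A subject who first reaches 37.5°C after 4 hours and stays on the device has a maintenance window under the criterion but is outside the synopsis population.

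For cooling, two sets will be reported and neither is defined or named as decisive. Because 9.3 ordinarily takes non-reachers off at 4 hours, a set of completers could leave out the failures. The whole-treatment condition would also turn a subject who cooled in time and stayed in band for 85% of steady state time into a cooling failure, although that subject meets both stated criteria.

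Section 6.8 relies on pre-specified success criteria to set bias aside. That argument needs the denominators fixed before the data are seen.

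**Working it through.** **The plan's own figure.** Section 6.6 uses p0 = 0.90, p1 = 0.75, z = 1.28 and 0.84:

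n = [(1.28·√(0.9·0.1) + 0.84·√(0.75·0.25)) / 0.15]² = [(0.384 + 0.364)/0.15]² = 24.85, rounded up to 25.

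The stated 25 reproduces and is not in dispute here.

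**Inputs.** Section 13.0 does not merge the flow cohorts, so the larger analysis set is N = 20 (double nostril, subjects 1–20). The threshold is 75%, reported with 90% confidence intervals. The interval method is not stated; exact Clopper–Pearson is assumed. Let X be the number normothermic by 4 hours and Y the number of those who also meet the maintenance criterion, with all X assumed to continue cooling. Late reachers are set aside. All counts are illustrative.

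**One data set, three readings of maintenance (X = 15, Y = 12).**

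| Reading | Proportion | Exact 90% CI |
|---|---|---|
| Synopsis: 4-hour responders | 12/15 = 80% | 56–94% |
| All treated, as 6.10 counts | 12/20 = 60% | 39–78% |
| 13.0 taken literally | 12/12 = 100% | not meaningful |

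**How often the first two disagree at N = 20.** Section 13.0 compares the proportion and its interval with 75% but does not say which decides, so both rules were checked.

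- *Observed proportion at least 75%, with cooling passing (X ≥ 15).* Responders pass if Y ≥ 0.75X; all treated pass if Y ≥ 15. They differ at X = 15 with Y = 12, 13, 14; X = 16 with Y = 12, 13, 14; X = 17 with Y = 13, 14; and X = 18 with Y = 14. That is 9 of the 111 possible (X, Y) pairs (16+17+18+19+20+21). They never differ at X = 19 or 20.
- *Lower 90% limit above 75%, with cooling also passing.* Cooling needs X ≥ 19 (lower limit 78.4% for 19/20, 71.7% for 18/20). The only disagreement is X = 19, Y = 18: 18/19 has lower limit 77.4%, 18/20 has 71.7%.

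The 9 pairs are not equally likely. If 75–90% of subjects reach by 4 hours and 75–90% of those hold (assumed rates, subjects independent), the chance of landing on one of them is about 13–37%.

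**First 10 subjects, with at least 8 reaching.** The readings differ at (X, Y) = (8, 6), (8, 7) and (9, 7). For example, 6/8 = 75% meets the synopsis proportion, while 6 of 10 misses the 8-of-10 count.

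**Cooling.** Suppose completed means the full scheduled time on the device, all non-reachers are removed at 4 hours, and all reachers complete (all assumed). Then 14 of 20 reaching gives 14/20 = 70% initiated and 14/14 = 100% completed. If 4 non-reachers are kept on under the 9.3 exception and complete, the completed figure is 14/18 = 77.8%.

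**The case against.** The strongest reply is that the 13.0 maintenance sentence is a drafting accident. It is ungrammatical, it shares its opening with the synopsis sentence, and the synopsis gives a workable population. That stands. A reader might infer that the plan would report a guaranteed 100%; the documents do not support that, because the sentence is evidently two merged into one. It still needs correcting, and the synopsis alone does not settle the matter while 6.10 counts the same endpoint differently.

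It can also be said that 6.10 is an interim rule for lengthening treatment, not the final analysis. That is right. Its denominator is fixed at 10, so the transition decision is unaffected. It is evidence of inconsistent counting and no more.

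A reader might infer that the 25 completing subjects in 6.6 make completers the analysis set, or that the plan intends to drop failures from the cooling result. Neither follows. The figure in 6.6 is a basis for a dropout allowance, 9.3 labels non-reachers as treatment failures, and the initiated set is reported as well. The 70% versus 100% contrast rests on an assumed definition.

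Finally, a reader might conclude that non-reachers must be scored as maintenance failures. The documents do not require it. The criterion runs from first reaching 37.5°C, and non-reachers already fail the cooling criterion. A conditional measure is defensible if declared in advance.

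**Conclusion.** The concern holds as a wording defect that affects who counts as a success, and it should be fixed before analysis. Three elements of 13.0 contradict other text outright: the 37°C start, the unrestricted time base, and the whole-treatment condition on cooling. The maintenance population in 13.0 is unusable as written and conflicts with the synopsis, and the deciding cooling set is not named.

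The effect is real but moderate. At N = 20 with cooling passing, 9 outcomes put the observed maintenance proportion on opposite sides of 75%; under a lower-limit rule one outcome does. In the lead example both intervals contain 75%, so the choice alters the headline proportion more than the strength of evidence. These results assume exact intervals, all 4-hour responders continuing cooling, and no late reachers. The 13–37% range rests on assumed rates as well.

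**What to change.** 1. In 13.0, change the start of the maintenance clock from 37°C to 37.5°C and the time base to steady state time. Remove the whole-treatment condition from the cooling success definition. Sections 6.3, 6.10 and 13.1 already agree with the result.
2. Replace the outcome-defined maintenance population with one stated denominator, worded identically in the synopsis and 13.0.
   - *Cooling:* the deciding set is every subject in the flow cohort in whom CoolStat was started, with those not at or below 37.5°C by 4 hours scored as failures. Define the completed set and label it supportive.
   - *Maintenance:* declare in advance either the synopsis responder set, labelled as conditional on reaching normothermia, or all treated, and report the other beside it. The choice is the sponsor's.
3. State how subjects who first reach 37.5°C after 4 hours, and those stopped early, are scored for maintenance.

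The cost is an edit to the synopsis and 13.0, with no new data. The reported proportions may be equal or lower than under the most favourable reading. Correcting the clock and time base can move individual results either way.

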NOTE 1: Throughout this protocol and case report forms, the term “investigator” may be used. In such circumstances only an approved sub-investigator or the PI may execute the action. These actions specifically include decisions to enroll, start COOLSTAT therapy, stop COOLSTAT therapy and withdrawal the subject for any reason. If any requirement is the sole jurisdiction of the Principal Investigator, it is specifically identified. The Site Principal Investigator will supervise the study and oversee that all clinical personnel assigned to this study have been trained to protocol requirements and device operation as necessary for their responsibilities.

Additional study investigators (sub-investigators) may be designated and supervised by the Site Principal Investigator and shall conform to the requirements described below, including providing their curriculum vitae.

PROTOCOL REVISION TABLES

Rev	Date	Prepared By	Reviewed By	Approved By
P2	10/13/17	---	---	
P3	8/8/18	[name]	[name]	[name]
P4	1/30/19	[name]	[name]	[name]
P5	6/10/19	[name]	[name]	[name]
P6	7/24/19	[name]	[name]	[name]
A	12/5/19	[name]	[name]	[name]
B	7/23/20	[name]	[name]	[name]
C	2/15/21	[name]	[name]	[name]
D	7/7/21	[name]	[name]	[name]

[figure not shown]
Rev	Details of Revision
P2	Original version approved by FDA for IDE and by UM IRB

P3	Added revision table, corrected all references to the definition of fever to $\geq 38.3^{\circ}\text{C}$ on pgs. 7, 25, 36, and 37; Added BMI range exclusion criteria on p.35; Fixed typo on p. 34
P4	Expanded indications to include seizure and metabolic encephalopathy on pgs. 6, 7, 8, 10, 16, 19, 23, 27, 32, 34, 38; Added SpotOn as core temperature probe on pgs. 10, 18, 19, 26, 32, 36, 37, 38, 39, 45; Allow otolaryngology residents to perform pre- and post-intervention nasal exams on pgs. 9, 11, 40, 52; Changed "systolic blood pressure" to "blood pressure" on pgs. 9, 10, 23, 26, 34, 37, 40, 50; Changed Product Designer to [name] on pg. 1.

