	
Phase 0 – Pre-Cooling Monitoring (30 minutes): Manual temperature (core and tympanic), ICP (when available) and blood pressure data collection every 5 minutes (and some additional observations, see above).
 
Phase 1 – Cooling Treatment: Manual data collection will occur at a minimum:
 
• 5 minute intervals for first 30 minutes of cooling period.• 30 minute intervals for first 8-hour cooling period.• 2 hour intervals for remaining 16 hour of cooling (if applicable). 
Phase 2 – Short-Term Post-Cooling Monitoring: Manual data collection will occur at 15 minute intervals during this 2-hour period immediately following COOLSTAT cooling.
 
Phase 3 – Long-Term Post-Cooling Monitoring: Manual data collection will occur at minimum four hour intervals through this 22-hour post-COOLSTAT cooling period.
 
Any additional data collections and the reasons for them shall be documented in the study case form.

Study Population	70 adult febrile patients in the neurosciences intensive care unit, with ischemic or hemorrhagic stroke, seizure, or metabolic encephalopathy. Hemorrhagic stroke includes both intracerebral hemorrhage and subarachnoid hemorrhage stroke. Only the first 30 subjects who meet post-consent eligibility criteria will receive COOLSTAT therapy.
Regimen	COOLSTAT® Transnasal Thermal Regulating Device will be applied to patients at a pressure not to exceed 30 cm H ₂ O (as automatically regulated by the device). A closed-loop control system in the COOLSTAT will modulate and control air flow and maintain the subject's core temperature between 36 °C and 37.5 °C, as measured by a hospital supplied embedded temperature sensor (esophageal, bladder, or 3M™ SpotOn™ temperature sensor). The device will be set to target of 36.5 °C.

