4.0 Indication for Use and Contraindications

4.1 Indication for Use

The CoolStat Transnasal Thermal Regulating Device is intended for temperature reduction to achieve normothermia, as an adjunct to anti-pyretic therapy, in adult patients with ischemic or hemorrhagic stroke, seizure or metabolic encephalopathy who are intubated and sedated. Hemorrhagic stroke includes both intracerebral hemorrhage and subarachnoid hemorrhage stroke.

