8.0 Study Inclusion and Exclusion Criteria

8.1 Inclusion Criteria

Male or female subjects may be included in the study if he/she meets ALL of the following inclusion criteria:

1. Admitted to the Neurosciences Critical Care Unit (NCCU).
2. Patient has ischemic or hemorrhagic stroke, seizure, or metabolic encephalopathy.
3. Patient is orally intubated or has tracheostomy tube and is mechanically ventilated.
4. Planned stay in NCCU > 24 hours.
5. Must have informed consent from the patient or the legally authorized representative (LAR) making decisions for the patient.

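### The exploratory subgroup analysis has strata only for ischemic and hemorrhagic stroke, so subjects treated for seizure or metabolic encephalopathy get no separate summary of cooling or adverse events

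*Combined protocol and SAP*

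**What the plan says.** Section 13.0 (Statistical Analysis Plan) names a single subgroup factor. The exploratory analysis is to be "stratified by stroke presentation (ischemic versus hemorrhagic"), and "Cooling performance and AEs will be evaluated by subgroup".

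The population is wider than that factor. Section 4.1 gives the indication as temperature reduction "in adult patients with ischemic or hemorrhagic stroke, seizure or metabolic encephalopathy who are intubated and sedated". Inclusion criterion 2 in section 8.1 reads "Patient has ischemic or hemorrhagic stroke, seizure, or metabolic encephalopathy". The study population row of section 1.0, the device description in 3.1 and the recruitment text in 7.1 list the same four diagnoses. Treatment is first come, first served, with no quota by diagnosis: "Only the first 30 subjects who meet post-consent eligibility criteria will receive COOLSTAT therapy".

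Section 13.0 also rules that "Double nostril air flow and single nostril air flow subjects will not be merged or directly compared". Subjects 1 to 20 form the double nostril cohort and subjects 21 to 30 the single nostril cohort.

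**The concern.** The sponsor has already decided that cooling and AEs should be looked at by presenting condition, but the two levels chosen describe only stroke. A subject who qualifies through seizure or metabolic encephalopathy alone has no stroke presentation and so cannot be placed.

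At stake is how complete the description is. Diagnosis has some bearing on safety in this protocol: sections 5.1.1, 5.2 and 9.3 tie the allowable blood pressure and intracranial pressure limits to the indication being treated. A reader of the final report who asks how many seizure or encephalopathy subjects were treated, how many reached normothermia and what events they had would find no planned output that answers.

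**Working it through.** **Coverage.** The check is mainly a comparison of sections.

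| Diagnosis | Indication (4.1) | Eligible (8.1) | Level in the subgroup factor (13.0) |
|---|---|---|---|
| Ischemic stroke | yes | yes | yes |
| Hemorrhagic stroke | yes | yes | yes |
| Seizure | yes | yes | none |
| Metabolic encephalopathy | yes | yes | none |

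Two of four diagnoses have no level. Sections 13.1 to 13.3 add no stratum, summary or listing by diagnosis, and neither does any other section.

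**Where these subjects do appear.** The cooling proportion in 13.0 and 13.1 is not restricted by diagnosis, so they count in it. They count in the maintenance proportion on the same terms as anyone else. Their events go into the table of all AEs described under Statistical Methodology in section 1.0, although that table has no diagnosis breakdown.

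**Sample size.** Diagnosis is not an input. The formula in section 6.6, with 0.90, 0.75, z = 1.28 and z = 0.84 as printed, gives

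n = [(1.28 × √(0.90 × 0.10) + 0.84 × √(0.75 × 0.25)) / 0.15]² = [(0.384 + 0.364) / 0.15]² = 24.85, rounded up to 25.

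This matches the stated 25. Changing the subgroup factor does not alter it.

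**How many subjects.** The documents give no figure, so the share s of treated subjects who qualify only through seizure or metabolic encephalopathy is an assumption. The expected number is N × s. The chance of at least one among 30, treating subjects as independent, is 1 − (1 − s)^30.

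| Assumed s | Of 30 treated | Of 20 double nostril | Of 10 single nostril | Chance of at least one in 30 |
|---|---|---|---|---|
| 10% | 3 | 2 | 1 | 0.958 |
| 20% | 6 | 4 | 2 | 0.999 |
| 30% | 9 | 6 | 3 | above 0.999 |
| 50% | 15 | 10 | 5 | above 0.999 |

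**Precision if all four diagnoses are shown.** The airflow cohorts stay separate. An equal four-way split, again assumed, gives 20/4 = 5 per diagnosis in the double nostril cohort and 10/4 = 2.5 in the single nostril cohort. Exact (Clopper-Pearson) 90% intervals for cells of that size are 0.34 to 0.99 for 4 of 5 and 0.37 to 1.00 for 3 of 3. Counts convey as much as such intervals do.

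**The case against.** The strongest reply is that section 13.0 never promises a breakdown by diagnosis. It poses one narrow exploratory question, ischemic against hemorrhagic stroke, and non-stroke subjects are outside that question by construction. On that reading the strata need not add up to the treated total. The trial is a feasibility study, and no hypothesis, success criterion or DSMB decision depends on diagnosis. This stands as a limit on importance, and it means the sentence is not an error in itself. It does not explain why the plan describes two of the eligible diagnoses separately and not the other two.

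Two practical objections also stand. Criterion 2 does not make the diagnoses mutually exclusive: a stroke patient with seizures meets it twice and may already sit in a stroke stratum, which would lower the number left out. And the history items in section 12.5 include stroke and seizures but not metabolic encephalopathy, so the qualifying diagnosis is not shown as a data field, although it has to be established when eligibility is confirmed under section 9.1.

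A reader might infer more than the documents support:

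- That the report would hold no cooling or safety data on these subjects. It would, in the overall proportions and the table of all AEs.
- That the report must support the indication for these diagnoses. Section 14.16 only leaves open the use of the data in later premarket notifications, among other uses.
- That the SAP sentence was missed when the diagnoses were added. The revision table dates that addition to P4, but it cannot show why the sentence reads as it does, and the point does not rest on it.

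**Conclusion.** The point holds as a gap in descriptive reporting. Under the plan as written, subjects who qualify only through seizure or metabolic encephalopathy are in neither stratum and get no separate summary of cooling or AEs.

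Its size is two of four diagnoses. The number of subjects is unknown, and 3 to 15 of 30 follows only from the assumed shares of 10% to 50%. At a share of 10% or more, at least one such subject is very likely. No primary proportion, confidence interval, sample size or success criterion changes. This is a minor improvement that costs almost nothing.

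**What to change.** In section 13.0, replace stroke presentation with qualifying diagnosis: ischemic stroke, hemorrhagic stroke, seizure, metabolic encephalopathy, with the last two combined if sparse. Add one line assigning each subject to a single primary qualifying diagnosis, recorded when eligibility is confirmed, so that a subject meeting criterion 2 in more than one way is counted once. Within each airflow cohort, report cooling success and AEs as counts or a subject listing by that diagnosis, so that every treated subject appears.

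The cost is the assignment rule, a field for the primary diagnosis if the forms lack one, and a few more table rows. The downside is very small cells; the text should say they are descriptive only. No extra subjects or assessments are needed.
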